COMIRB Protocol

Colorado Multiple Institutional Review Board; [name]; [contact]

Protocol #: 15-0474

Project Title: Dysregulation of FSH in Obesity: Functional and Statistical Analysis

Principal Investigator: [name]

Version Date: v06-October-2020

I. Hypotheses and Specific Aims:

Hypothesis. *Insufficient FSH pulsatility, as seen in obesity, results in inadequate folliculogenesis and reduced ovarian steroid and protein production.*

AIM: *To test the hypothesis that insufficient FSH pulsatility, as seen in obesity, results in inadequate folliculogenesis and reduced ovarian steroid and protein production.* We will determine if exogenous FSH administered in a pulsatile fashion results in a significant increase of ovarian hormones in obese women. Serial inhibin B and E2 levels will be measured in obese and normal weight women undergoing frequent blood sampling studies before and after GnRH antagonist blockade. In addition, we will conduct a pilot study to correlate the fecal microbiome and bacterial metabolism with reproductive hormone levels in normal weight and obese women.

II. Background and Significance:

Maternal obesity is an independent risk factor for decreased reproductive fitness and detrimental impact on offspring. In the US, 32% of women 20 to 39 years old are obese.¹ U.S. women born in the 1980s exhibit a 21 % higher propensity to have a large body mass compared to those born in the 1960s.² Thus, a further escalation of the current trends is expected when the 1980s generation reaches its peak of obesity prevalence. Maternal obesity is associated with decreased reproductive fitness: ovulatory and menstrual dysfunction,³ increased congenital anomalies,⁴ iatrogenic⁵ and spontaneous⁶ preterm birth, recurrent miscarriage.⁷ Even in regularly ovulating women, obesity is linked with increased spontaneous pregnancy loss,⁸ longer time to pregnancy,⁹ and decreased lifetime fertility.¹⁰

Although weight loss and lifestyle modifications should be the first line therapy for any sequelae of obesity, the evidence for the effectiveness of this approach for impaired reproduction is lacking. A recent Cochrane meta-analysis indicated that there are no randomized trials supporting a benefit of weight loss for pregnancy outcomes.¹¹ Thus, it is critically important that we improve our understanding of the pathophysiology leading to decreased reproductive fitness in obesity in order to design alternative approaches for intervening. Abnormalities of reproductive hormones and ovarian function have been implicated.¹²⁻¹⁵ Our long-term goal is to identify molecular interactions between affected aspects of hypothalamic-pituitary-ovarian (HPO) hormonal changes and pathophysiology of obesity. However, to target molecular interactions we must clarify the mechanisms for altered HPO dynamics in this population. Thus, our short-term goal is to improve our understanding of the mechanisms underlying disrupted reproductive hormone secretion in obese women.

Pituitary follicle-stimulating hormone (FSH) secretion is regulated mostly by hypothalamic Gonadotropin-releasing hormone (GnRH) secretion but also by endocrine input from the ovary. Inhibins, secreted by granulosa cells of ovarian follicles, exert a potent negative feedback effect on FSH. The reproductive aging associated fall in circulating inhibin B (and not a drop in estradiol) is believed to be responsible for the classic, monotropic rise in FSH that accompanies the menopausal transition. FSH pulsatility is challenging to characterize given its long half-life and low signal-to-noise ratio. Our work shows that existing pulsatility methods miss a third or more of FSH pulses. Female obesity is associated with reduced levels of both inhibin B and FSH, providing a unique opportunity to tease apart the secretory dynamics of FSH in the absence of one of its controlling mechanisms. Female adiposity is strongly related to decreased reproductive fitness, subfertility, and harmful metabolic programming of the offspring. Reproductive dysfunction in obesity may be related to abnormal hypothalamic-pituitary dynamics (a central deficit in GnRH, FSH or luteinizing hormone (LH) production), an abnormal ovarian environment (reduced sex steroid or ovarian protein production), or both. Most analyses of FSH have focused on mean levels, leaving us unable to probe if features of pulsatile FSH secretion are related to the reproductive deficits observed in obese women. Thus, a knowledge gap exists because we have not adequately assessed the interplay between pituitary FSH and its feedback in obesity.

There is abundant evidence that the fecal microbiome is altered in obesity and may be a contributing factor to its etiology. To date no studies have correlated measurements of ovarian steroids with microbiome composition and/or bacterial gut metabolism. Evidence in mice suggests that bacterial de-conjugation of estrogen glucuronides may modulate circulating estrogen levels^{18,19}. We propose to analyze the fecal microbiome of normal and obese women and correlate bacterial composition and metabolism with host reproductive hormone levels before and after treatment. This will provide preliminary data to test the impact of microbial diversity on obesity related sub-fertility.

III. Preliminary Studies/Progress Report:

Our new preliminary data from [name] lab (co-I) demonstrate that pulsatile FSH secretion dramatically enhances ovarian function in mice (PNAS 2014;111:5735). In this transgenic model, FSH was diverted into the LH secretory pathway that resulted in reduced follicular atresia, prolonged reproductive lifespan and enhanced fertility. The oocytes produced in these FSH transgenic mice were of high quality, developed into viable blastocysts, and resulted in viable pups upon embryo transfer. We aim to translate and expand these novel findings of biological relevance of FSH pulsatility in the current proposal.

[figure not shown]
The PI has recently conducted a study recruiting women from the local community for an investigation of pituitary sensitivity to estrogen in obesity (National Clinical Trial (NCT) identifier: 01381016). Significantly lower serum inhibin B level was observed in obese women.

Reduced Early Follicular Inhibin B in Obese Women despite "Un-elevated" Serum FSH

	Normal weight n=10	Obese, n=11	P
Age, years	29.4(1.9)	32.5 (1.8)	0.25
BMI, kg/m ²	21.2 (1.5)	36.7 (1.3)	<0.01
AMH, ng/ml	3.2 (2.3)	1.2(1.1)	0.01
Inhibin A, pg/ml	19.3(6.6)	20.2 (6.1)	0.87
Inhibin B, pg/ml	96.6 (36.3)	67.7(38.2)	0.04
Mean FSH, IU/L	6.4 (0.7)	5.8(0.8)	0.57
Mean LH, IU/L	5.2 (0.8)	2.5 (0.2)	<0.01

Notably, antral follicle count is typically NOT reduced in obese women as seen by others and our group. Thus, the reduced inhibin B is unexplained. In this Aim, we will determine whether the pulsatile pattern of FSH secretion is responsible for the reduced circulating levels of inhibin B and E2 in obese women. We and others have shown that the deficit in LH in obesity is greater than the FSH deficit.

However, FSH deficit in obese women appears to be modifiable. We have observed a significantly improved FSH but not LH response to IV GnRH in obese women after one month of transdermal estrogen.

Exogenous Estradiol Improves FSH Sensitivity in Obese Women. Composite response of mean endogenous LH and FSH (\pm SEM) for 11 obese and 10 normal weight menstruating women to GnRH bolus of 75 ng/kg given at time =360. Y axis is gonadotropin in IU/ml. X axis is time on minutes.

This suggests that the pituitary is a functionally important locus for mediating the impact of obesity on female reproduction. We posit that abnormal FSH secretion is responsible for ovulatory defects in obesity and is the focus of the current proposal.

IV. Research Methods

A. Outcome Measure(s):

We will examine LH and FSH secretion during frequent blood sampling at 10 min intervals.

Primary: the difference between peak E2 and inhibin B from Day 1 to day 2. This is defined as the maximum hormone value during the Day2 study minutes after the maximum hormone value during the Day1 study before GnRH antagonist is administered.

Secondary: peak inhibin B and E2 per subject, area under the curve (AUC) for inhibin B and E2 during stimulation; we will compute LH and FSH pulsatility (pulse frequency, and average pulse amplitude) on day 1 and day 2, along with the means of LH and FSH to assess adequacy of GnRH antagonism and FSH stimulation. LH pulsatility will be assessed to confirm phenotypic concordance of this study population with existing literature.

B. Description of Population to be Enrolled:

Inclusion criteria:

- Age between 21 to 39 years old with regular menstrual cycles every 25-40 days,
- Body mass of 18.5 kg/m²-24.9kg/m² (normal weight controls) or greater than 30.0 kg/m² (obese group),
- Prolactin and TSH within normal laboratory ranges at screening, baseline hemoglobin >11 gm/dl.

Exclusion criteria:

- Diagnosis of PCOS, defined by the 2003 Rotterdam criteria as suggested by 2012 NIH Workshop,
- History of chronic disease affecting hormone production, metabolism or clearance or use of thiazolidinediones or metformin (known to interact with reproductive hormones),

- Use of hormones affecting HPO axis (such as hormonal contraceptives) within 3 months of entry,
- Strenuous exercise (>4 hours of intense physical activity per week),
- Pregnancy, breast-feeding or current attempts to conceive, significant recent weight loss or gain,
- Irregularities in uterus or ovaries,
- Serum anti-Mullerian hormone (AMH) equal to or greater than 20 pmol/l. This is based on the data that the specificity and sensitivity of AMH for identifying women with polycystic ovary syndrome were described to be over 97% and 95%, respectively, at this cut-off (Eilertsen et al., Hum Reprod 2012; 27: 2494-2502). Additionally, it has been demonstrated that AMH and antral follicle count (AFC) have an equal level of accuracy in the prediction of an excessive response to ovarian stimulation (Broer et al., Hum Reprod Update 2011;17:46-54) but AFC is subject to inter-observer variability (J. van Disseldorp et al., Hum. Reprod 2010; 25: 221-227),
- Impaired renal, hepatic, or cardiac function,
- Allergy, hypersensitivity, or intolerance to study drug or its excipients
- Presence or sequelae of gastrointestinal, liver, kidney, or other conditions known to interfere with absorption, distribution, metabolism, or excretion of drugs,
- Recent blood or blood product donation.

C. Study Design and Research Methods

Up to 68 subjects will undergo two 10-hour frequent blood sampling studies on consecutive days. However, the PI will first need to identify the dose level that results in a significant pharmacodynamic (PD) effect, namely an increase in serum inhibin B, with a target PD response rate of 80% across patients. Therefore, up to 9 subjects will also be needed for a pilot portion of the study (up to 3 subjects at each level will be needed to identify the level at which the target response rate is reached).

The total maximum number of subjects consented will be 120.

At the date of this protocol (10/11/2016), 6 subjects had already been treated in the pilot portion of this protocol.

- 3 subjects were treated at 10 IU; none of them showed an increase in inhibin B; adverse events of delayed menses and hot flushes thought be related to GnRH antagonist use were reported.
- 3 subjects were treated at 20 IU; none of them showed an increase in inhibin B; adverse events of delayed menses and hot flushes thought be related to GnRH antagonist use were reported.

With this version of the protocol (10/11/2016), we propose to treat 9 subjects with 30 IU, administered every 60 minutes over 10 hours, for a total of 300 IU.

Preliminary analysis of the completed study visits thus far (09/3/2019) have indicated the obese cohort has lower serum FSH levels than the normal weight cohort in response to the addition of rFSH on Day 2. We want to investigate if the difference we see is because FSH is being excreted in urine. We propose to collect urine at 4 nonspecific time points during day 1 to obtain a baseline value of FSH in urine for each participant and at the following specific time points T=0, 30, 60, 120, 240, 480, 600 minutes during day 2. We understand that asking the participants to provide 3 urine samples in the first hour of day 2 might not be possible for every participant. Therefore, we will ask each participant to give at least 2 samples (0 and 60 min on day 2) and request the 30-minute sample be tried but not required.

(09/18/2019) Due to the pilot phases needing more participants than originally estimated, the fact that we have seen co-morbidities in the high BMI cohort which causes more screen fails than the normal BMI cohort and the difficulty scheduling the study visit in the Inpatient CTRC we need to increase the total enrolled number to 90 from 77.

(02/19/2020) We have still been experiencing difficulty in scheduling the study visits at the inpatient CTRC. Specifically, we only can schedule a minimum of 3 months in advance. This has caused some participants to drop due to the long time between the screening visit and the study visit. An accurate prediction of the start of a participant's period is difficult 3 months in advance. We have also seen an increase in loss to follow-up.

Prior to the initiation of the frequent blood sampling, the subject will undergo a screening visit where they will sign the consent, and have a history and physical exam, including a pelvic exam, and a blood draw. Screening labs will include liver function tests and renal function tests. The PI will determine eligibility based on the laboratory values, exam, and medical history. Due to COVID-19 we are adding the option to move part of the screening visit to a Telehealth virtual visit through EPIC or via a Zoom meeting, if necessary. The parts conducted virtually would be the reading of the consent, answering of the participant's questions and the participant's history (after verbal agreement by the participant of consent into the study). We will ask the participant to print and sign the consent and email a scanned copy or a photo taken with their cell phone to us and we will send back a copy with both signatures before the next steps of the screening visit are scheduled. The height and weight, the hip/waist circumference and the screening blood draw will be performed in the outpatient CTRC and will occur after the consent is signed. The participant will come into the outpatient CTRC clinic to complete the aforementioned procedures. The study team will keep their interaction with the subject to a minimum at this visit.

If eligible, the two-day visit will be scheduled to correspond with the subject's early follicular phase (cycle days 3-6). To help predict the date of their study visit we will provide the participants with urine ovulation tests strips to voluntary use. We will ask the participant to start using 8-10 days after the ending date of their last period. We will ask them to use these urine ovulation tests in the morning. Once they observe a positive with the ovulation test strip we will ask them to notify the research coordinator. The study visit will then be scheduled. Prior to the study visit the participant will be asked to provide an optional fecal sample using the Alpco EasySampler® Stool Collection Kit and will be asked to bring it to the study visit in a pre-provided thermal transport bag. Participants will be instructed to freeze the fecal sample after it is collected.

Women will report to the CTRC at 1:30pm on day 1 of the study for placement of an indwelling IV catheter. Prior to initiation of the study drug a serum pregnancy test will be done to rule out the possibility pregnancy. Small volumes (3-4mL) blood samples will be drawn every 10 minutes for 10 hours (2pm – 12am) to assess pituitary gonadotropin dynamics. During the first 10 hours of the study we will collect the participants urine 4 times (non-specific) to assess endogenous FSH elimination in their urine. After the first 10 hours of blood samples have been collected, the GnRH antagonist Cetorelix will be given subcutaneously (3 mg). The subject will then be allowed to sleep until 6am.

On day 2, at 6am a second, smaller dose of Cetorelix (0.25mg) will be given at subcutaneously. In addition, beginning at 6 am, small volume blood samples will again be drawn every 10 minutes for 10 hours. Repeated boluses of exogenous recombinant FSH (rFSH) will be given by IV during this 10-hour visit. Urine will also be collected during day 2 at the following specific time points: T=0, 30, 60, 120, 240, 480, 600. If the participant cannot give 3 urine samples in the first hour of Day 2 we will request at least two samples during the first hour instead of 3. Where the 30 minute will be requested, but optional. Final blood samples will be collected after the last dose of FSH. At about 4pm, the visit will conclude, and the subject will be discharged from the clinic. Subjects will be advised to use double barrier contraception until the following menses to prevent conception immediately following the study.

Subjects will also be provided a second Alpco EasySampler® Stool Collection Kit and be asked to return an optional stool sample within 7 days of the study visit.

All subjects who received 30 IU of the rFSH will have safety follow up phone calls the next day, 3-5 days and 7-10 calendar days after discharge from the clinic. Any adverse events identified during that call will be reported and followed until resolution.

Patient confidentiality. Patient confidentiality will be respected and guarded by adhering to HIPAA guidelines for personal health information. We will describe this approach to study subjects both verbally and in the informed consent document. They will be told that their information will be made available to appropriate representatives of the National Institutes of Health who may be reviewing the records in accordance with accepted policies and procedures. This approach has been successfully utilized by us previously for numerous clinical research studies at our institution, including the studies directed or co-directed by the PI. No breaches of patient confidentiality or inappropriate disclosure of their medical information have transpired. All participants will be given a study number that will identify their file. Files will be kept in the Clinical and Translational Research Center, under lock and key, or in the PI or research coordinator's office. Identifying information other than the study number will be redacted from participant's study records such that the file cannot be linked to the participant by name. The code linking study numbers to name will be kept by the research coordinator in a separate folder in a separate locked cabinet in a locked office. No identifying information will be released in the course of publication or presentation of study findings.

Samples will be sent to the University of Virginia to run the inhibin B assay as UVA has one of the most sensitive and precise assays for inhibin B. No identifiers will accompany the samples when sent to UVA.

E. Data Analysis Plan:

- 1) To test whether the difference in maximal inhibin B and E2 response between day 1 and day 2 depends on group (obese vs. normal weight) we will use a two-sample t-test.
- 2) In a second phase of analysis, we will adjust for potential confounders such as age and AMH level. We will repeat this analysis on the other secondary outcome measures.
- 3) To understand how inhibin B and E2 respond to FSH stimulation after GnRH antagonist we will compare groups in relation to the maximal change in inhibin B.
- 4) To understand how changes in inhibin B relate to changes in estradiol, linear regression will be used to assess whether the maximal change in inhibin B between day 1 and day 2 is statistically associated with the change in maximal E2 response between day 1 and day 2 (i.e. $\Delta MaxE2 = \beta_0 + \beta_1 \Delta Inhibin B$).
- 5) To characterize the changes in the microbiome we will analyze bacterial diversity by 16s ribosomal RNA sequencing. We have extensive experience in the analysis of the human microbiome in the environment, nares, vaginal, and intestinal tract and will analyze our data as previously described.²⁰⁻²² Microbiome data will be used for exploratory analyses in relation to clinical and other parameters measured among the study participants.

Pilot:

We are planning to assess the change in inhibin B levels following repeated bolus dosing of recombinant FSH (rFHS) following GnRH antagonist blockade. For the purposes of this study, we are interested in identifying the dose level that results in a significant pharmacodynamic (PD) effect, namely an increase in serum inhibin B, with a target PD response rate of 80% across patients. Statistical significance for the PD response at the patient level will be identified as an increase of 2.3 times the baseline standard deviation for inhibin B measurement in normal women. Using the data provided in the above table, showing a standard deviation in serum inhibin B concentration in normal women of 36.3 pg/mL, an increase in serum inhibin B of 83.5 pg/mL following FSH dosing would be considered a significant PD effect. This value provides a one-sided statistical significance at the 0.05 significance level, appropriate as there is an *a priori* anticipation that the response will occur in only one direction.¹⁶ To determine statistical significance of the dose level of 10 IU IV every 60 minutes, three study subjects will

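### The secondary AUC for inhibin B and E2 covers Day 2 only, so a lower value in obese women would be expected from their lower starting level even without any response to rFSH

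*Combined protocol and SAP*

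**What the plan says.** - **Secondary outcomes (IV.A):** "peak inhibin B and E2 per subject, area under the curve (AUC) for inhibin B and E2 during stimulation". In IV.C rFSH is given only on Day 2, so the AUC is a Day 2 quantity. No day is named for the peak.
- **Primary outcome (IV.A):** "the difference between peak E2 and inhibin B from Day 1 to day 2". This one is referenced to Day 1.
- **Gonadotropins (IV.A, same sentence as the AUC):** "we will compute LH and FSH pulsatility (pulse frequency, and average pulse amplitude) on day 1 and day 2". Both days are named here but not for the AUC.
- **Analysis (IV.E, items 1 and 2):** the primary comparison is a two-sample t-test of obese against normal weight. A second phase adjusts for confounders, with age and AMH given as examples, followed by "We will repeat this analysis on the other secondary outcome measures". The Day 1 hormone level is not named.
- **Premise (III):** "Significantly lower serum inhibin B level was observed in obese women". The same section sets out to learn whether the FSH pulse pattern is "responsible for the reduced circulating levels of inhibin B and E2 in obese women". The table gives inhibin B by group but has no row for E2.

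**The concern.** The aim in Section I is to learn whether pulsatile rFSH raises ovarian hormones. A total AUC over 10 hours adds up the level a woman brought into Day 2 and whatever rFSH added. If the groups differ beforehand, as the protocol assumes, the AUC will tend to differ whether or not the ovaries respond differently.

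A lower AUC under stimulation in obese women could then be read as a blunted response, and as support for the primary result, when it only restates the starting deficit. Little or no response is a realistic case. The pilot text in IV.E reports changes of +9%, +13% and a decrease at 10 IU, and +38.5%, +13.2% and a decrease at 20 IU.

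**Working it through.** **Inputs.** From the table in III: normal weight n = 10, inhibin B 96.6 (36.3); obese n = 11, 67.7 (38.2) pg/mL. The pilot text in IV.E describes its figure as "showing a standard deviation in serum inhibin B concentration in normal women of 36.3 pg/mL", so the bracketed values are read as SDs. From IV.C: up to 68 women, sampled every 10 minutes for 10 hours on each day. Assumed, because not stated: 34 per group, two-sided alpha of 0.05.

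**1. The plan's own P value.** Pooled SD = √[(9 × 36.3² + 10 × 38.2²)/19] = 37.3. The gap is 96.6 − 67.7 = 28.9, with SE 37.3 × √(1/10 + 1/11) = 16.3. So t = 28.9/16.3 = 1.77 on 19 df, P = 0.09 (Welch also 0.09), 95% CI −5.2 to 63.0. The stated 0.04 is not reproduced. One-sided t gives 0.046, a z-test 0.076, and reading the brackets as SEMs 0.59. A rank test cannot be checked from summaries.

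**2. AUC with no response.** With flat levels at the table means, AUC is 10 × 96.6 = 966 against 10 × 67.7 = 677 pg·h/mL. The difference is 289, so obese women are 30% lower. Standardised, 28.9/37.3 = 0.77.

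**3. How often that is significant.** Noncentrality is 0.77 × √(n/2), which is 3.19 at n = 34. Noncentral-t results with no rFSH response in either group:

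| Women per group | Share of gap persisting on Day 2 (SD unchanged) | Trials with a significant difference |
|---|---|---|
| 34 | 100% | 88% |
| 34 | 75% | 66% |
| 34 | 50% | 35% |
| 34 | 25% | 12% |
| 25 | 100% | 77% |
| 20 | 100% | 67% |
| 15 | 100% | 54% |

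If the antagonist instead scales every woman's level by the same factor, mean and SD shrink together. The standardised gap stays at 0.77 and the 88% stands.

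**4. Which Day 1 reference removes the artefact.** Suppose every woman falls to 75% of Day 1. Day 2 minus Day 1 is then −0.25 × 966 = −241.5 in normal-weight women and −0.25 × 677 = −169.3 in obese women. Subtraction now makes obese women look better by 72 pg·h/mL, while the ratio is 0.75 in both. I simulated no response with lognormal levels matched to the table, 34 per group, Day 1–Day 2 correlation 0.8 and 0.95, and 20,000 trials per scenario:

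| Day 2 level as share of Day 1 | Raw Day 2 AUC lower in obese | Difference rejects | Log ratio rejects |
|---|---|---|---|
| 100% | 87% | 5% | 5% |
| 75% | 87% | 26–56% | 5% |
| 50% | 87–88% | 65–81% | 5% |

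Under suppression, essentially all rejections of the difference favour obese women. Adjusting Day 2 for Day 1 by ANCOVA (normal data) rejected in about 7–8% of trials at correlation 0.95 and 16–17% at 0.8.

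**5. Limit of the ratio.** If the antagonist removes the same absolute amount from everyone, the ratio is the biased measure. A common fall of 28.9 gives 67.7/96.6 = 0.70 against 38.8/67.7 = 0.57. This is why the difference belongs beside it.

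**The case against.** **The gap may be smaller here, or absent.** It comes from 21 women in another study and its interval includes zero. The antagonist is given between the two days, so the share that survives is unknown. This trial also excludes AMH of 20 pmol/l or more. The earlier normal-weight mean of 3.2 ng/ml exceeds that cut-off at any conversion factor above 20/3.2 = 6.25 (the documents give no factor), so the new controls may be a truncated group. This stands. A reader might infer that obese women will certainly show a lower AUC, but the documents support only an expectation.

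**The planned analysis may be adjusted.** The sentence extending the analysis to the secondary outcomes follows the one on confounders, and that list is open. AMH differs between groups (3.2 against 1.2 ng/ml), so adjustment may absorb some of the gap. This stands, by an unknown amount. The 88% describes the unadjusted test.

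**A real response would swamp the gap.** The pilot criterion is 2.3 × 36.3 = 83.5 pg/mL, about 2.9 times 28.9. This stands only in part. If both groups gained 83.5 throughout, the AUCs would be 1,801 and 1,512, still 289 apart.

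**The peak is already handled.** A reader might extend the criticism equally to the peak. The documents do not support that, because the Day 1-referenced peak is the primary outcome. The secondary peak lacks only a named day.

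**Nothing labels the AUC a measure of response.** True, but the plan names no other purpose for it, and the aim concerns response.

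**Conclusion.** The point holds, mainly for the AUC. As written, a between-group comparison of Day 2 AUC cannot separate starting level from response, and on the protocol's own premise it leans towards a lower value in obese women. With no response, a significant lower inhibin B AUC would appear in about 88% of trials if the full gap persists at 34 per group. It would appear in 54–77% at 15–25 per group, and in 66% down to 12% as the retained share falls from 75% to 25% with the SD unchanged. These figures assume an equal split, a two-sided 0.05 level, no covariates, and table brackets that are SDs.

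Two stronger readings are not supported. For E2 the documents assert a deficit but give no group figures, so only the direction can be claimed. Nor is plain subtraction of Day 1 a safe cure, given how it behaves under proportional suppression. The effect is confined to secondary outcomes, but it changes what the AUC result could be taken to show.

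**What to change.** In IV.A, define AUC for inhibin B and E2 on both days over the same 10-hour sampling length. In IV.E, make the between-group comparison of log(AUC Day 2/AUC Day 1) the lead analysis. Report the plain difference beside it, and state in advance that disagreement between the two will be read as uncertainty about how the antagonist lowers levels, not as evidence of a group difference in response. Report Day 2-only AUC descriptively. Name the day or days for the secondary peak, and say that its Day 1-referenced form is the primary outcome. Label the brackets in the preliminary table as SD or SEM, and name the test behind P = 0.04.

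The cost is a few lines of text. Day 1 blood is already drawn every 10 minutes, and the primary outcome already needs inhibin B and E2 measured on Day 1. More Day 1 assays may be needed if they were not planned at the Day 2 density, which the documents do not state. One limitation remains: Day 1 runs from 2pm to 12am and Day 2 from 6am to 4pm, so any time-of-day effect is part of the ratio. It biases the group comparison only if it differs between groups.

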Appendix: Study Visits and Procedures Flow Chart

SAFETY Follow Up phone calls (24 hours, 3-5 days and 7-10 post-discharge)

** All blood draws conducted by CTRC Inpatient or Outpatient staff

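### The last scheduled safety call falls 9 to 30 days before the next period is due, so no call can detect delayed menses, a known adverse event of this regimen

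*Combined protocol and SAP*

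**What the plan says.** Section IV.C sets the safety follow-up for every subject who received 30 IU of rFSH: "safety follow up phone calls the next day, 3-5 days and 7-10 calendar days after discharge from the clinic". Adverse events found at a call are then followed to resolution. What is readable of the Appendix flow chart repeats the schedule: "SAFETY Follow Up phone calls (24 hours, 3-5 days and 7-10 post-discharge". The only other contact after discharge in the available text is an optional stool sample within 7 days.

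The timing within the cycle comes from two other places. Section IV.B requires "Age between 21 to 39 years old with regular menstrual cycles every 25-40 days". Section IV.C states that "the two-day visit will be scheduled to correspond with the subject's early follicular phase (cycle days 3-6"), with discharge at about 4pm on the second day.

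On known adverse events, section IV.C says of the 10 IU cohort, and again of the 20 IU cohort, that "adverse events of delayed menses and hot flushes thought be related to GnRH antagonist use were reported". The antagonist is part of the standard procedures: after the day 1 sampling "the GnRH antagonist Cetorelix will be given subcutaneously (3 mg"), with a further 0.25 mg on the morning of day 2.

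On pregnancy, "Prior to initiation of the study drug a serum pregnancy test will be done", and after discharge "Subjects will be advised to use double barrier contraception until the following menses".

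**The concern.** A late period can be recognised only once its due date has passed. If every call comes before that date, the schedule can pick up early hot flushes but not the other adverse event that the protocol itself attributes to the study regimen. The follow-to-resolution rule does not help, because it starts from an event identified at a call.

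Two things are at stake, both modest. For women still to be treated, the record of a known drug-attributed event may be incomplete. And when a period is late, no scheduled step separates drug-related delay from pregnancy, because the only pregnancy test in the available text precedes study drug. The contraception advice runs to the next menses whether or not anyone calls; a contact would simply confirm that this period has ended.

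The efficacy outcomes and the pilot decision rule are not touched. Nor is any harm claimed to the nine-subject safety package for FDA. That step belongs to the 10/11/2016 revision, and section IV.C was already comparing obese and normal-weight subjects from completed visits by 09/3/2019, so the package was probably submitted before this October 2020 version.

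**Working it through.** The plan states no interval from discharge to next menses, so there is no figure of its own to reproduce. The check is a day count.

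**Inputs**
- Visit timing: cycle days 3-6 (IV.C).
- Discharge: second study day (IV.C).
- Cycle length L: 25 to 40 days (IV.B).
- Last call: 7 to 10 days after discharge (IV.C and Appendix).
- Assumption: the woman's usual cycle length would hold in the treated cycle. A drug-induced delay only widens the gap.

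**Discharge day.** If study day 1 falls on cycle day 3-6, discharge is on cycle day 3 + 1 = 4 to 6 + 1 = 7. If both study days must fall within cycle days 3-6, it is cycle day 4 to 6.

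**Last call.** Earliest 4 + 7 = cycle day 11; latest 7 + 10 = cycle day 17.

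**Next menses.** Bleeding starts on cycle day L + 1, so days from discharge = L + 1 − discharge day.
- Shortest: 25 + 1 − 7 = 19.
- Longest: 40 + 1 − 4 = 37.
- For a 28-day cycle: 29 − 7 = 22 to 29 − 4 = 25.

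**Gap from last call to due date.** Shortest 19 − 10 = 9 days; longest 37 − 7 = 30 days.

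**Other readings**

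| Reading | Menses due after discharge | Shortest gap after last call |
|---|---|---|
| Study day 1 on cycle day 3-6 | 19-37 days | 9 days |
| Both study days within cycle days 3-6 | 20-37 days | 10 days |
| First reading, menses counted on day L | 18-36 days | 18 − 10 = 8 days |

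Under every reading, 0 of the 3 calls reaches the due date.

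The number of missed events cannot be estimated: the documents give no count or rate of delayed menses at either lower dose.

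**The case against.** The strongest reply is that the event was recorded without these calls. Delayed menses was reported at 10 IU and 20 IU, while the call schedule is written for 30 IU subjects. These women cycle regularly, work with the coordinator on the timing of their periods and are told to use contraception until the next one, so they have reason to notice a delay. This stands as evidence that the event can come to light unprompted. It does not show that capture is complete, and the documents do not say how the lower-dose reports were collected.

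A second reply is that the calls are tied to the 30 IU rFSH dose, for which 7-10 days may be long enough, whereas delayed menses was attributed to the antagonist. That may explain the schedule. But 30 IU subjects receive the antagonist too, and no other scheduled contact covers its late effect.

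Third, the text is incomplete: section IV runs A, B, C, E, most of the flow chart is missing, and the consent pages were removed. A later contact, or an instruction to report a late period, may sit there. This limit is real. Against it, section IV.C and the readable flow-chart text agree on the call schedule, and neither lists a later call.

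Finally, the pregnancy argument is limited. Women trying to conceive are excluded, a test precedes dosing and double barrier contraception is advised. It supports a contact after the due date but would not carry the point alone.

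**Conclusion.** The point holds as a minor gap in scheduled safety follow-up. On the available text, the last call to a 30 IU subject comes 9 to 30 days before her next period is due, and none of the three calls can detect delayed menses. The result rests on the stated visit window and cycle lengths and does not depend on how cycle days are counted. That the record may be incomplete is an inference from the schedule; no missed event is documented. If a later contact exists in the unavailable pages, the sponsor need only point to it.

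**What to change.** For all remaining 30 IU subjects, add one call or secure message about a week after the expected menses date, worked out from the woman's usual cycle length, and record the date of first bleeding. That falls 19 + 7 = 26 to 37 + 7 = 44 days after discharge. If she has not bled, make one repeat contact a week later (33 to 51 days after discharge), advise a pregnancy test, and follow the delay as an adverse event under the existing rule. The one-week margin is a proposal, since the plan sets no threshold for calling menses delayed.

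The cost is one or two short contacts per woman on top of the three existing calls. The number still to be treated is not stated. As an upper bound, if all of the up to 68 main-study subjects were still to come, that is 68 × 1 = 68 to 68 × 2 = 136 contacts. At an assumed 5 to 15 minutes each, the total is 68 × 5/60 = 5.7 to 136 × 15/60 = 34 coordinator hours. Scheduled follow-up ends 9 + 7 = 16 to 30 + 7 = 37 days later than now, or 23 to 44 days later with the repeat. Some late contacts will fail. Treatment, visits and blood sampling do not change.
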